5.3.2. Sensitivity Efficacy (sub-group) analysis

The secondary set of subjects for exploratory efficacy is the set of all seropositive subjects who were positive for the presence of trypanosome (*Tb spp.*) by at least one method in skin, blood and/or DBS at baseline. The analysis will be repeated considering type of sample skin, blood or DBS separately. Secondary diagnostic parameters are occurrence of positive results by IHC in skin, by TBR-PCR, 18S-PCR in skin, blood and/or DBS, as well as by any novel diagnostic parameters corresponding to occurrence of positive results by multiplex qPCRs, multiplex RT-qPCRs and/or SHERLOCK in skin, blood and/or DBS. The secondary analyses will be the same as the primary

diagnostic analysis, as the main sensitivity analysis will be performed on the subgroup of positive dermal trypanosome subjects at entry (Secondary exploratory diagnostic Analysis). Missing data at month 4 will not be imputed to avoid loss of sensitivity of test (exploratory analysis of observed cases). However, a sensitivity analysis will assess the robustness of the primary analyses after imputation of a failure (positive diagnosis and presence of symptoms accordingly) in case of missing information.

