Planned analyses	
 
Study populations
 
For the main safety study, the study populations that will be used for the analyses are defined as below:
 
Safety set of subjects (SS) is a modified intent to treat (mITT) set of subjects composed of all randomised subjects who received at least one tablet of IP (placebo or acoziborole).
 

	
 
For the TrypSkin sub-study, the study populations that will be used for the analyses are:
 
Primary set of subjects: for exploratory efficacy analyses is the mITT set composed of subjects, who participate in the TrypSkin sub-study and who receive at least one dose of IP (placebo or acoziborole).
 
Secondary set of subjects: for exploratory efficacy analyses is the set of all seropositive subjects who are positive for T.b. gambiense by at least one molecular diagnostic test in the skin , blood and/or DBS at baseline.
 

	Primary endpoint analysis Adverse events will be coded using the Medical Dictionary for Regulatory Activities (MedDRA) system organ class (SOC) and preferred term (PT). Occurrence rates of each TEAE (≥1%), by MedDRA PT, will be compared. The primary outcome measure is the excess rate (ER) of TEAEs over the first 4 months post-treatment in the acoziborole group compared with placebo. The occurrence rate will be the number of subjects with at least one TEAE as the numerator and the number of subjects who receive at least one tablet of study medication (the SS) as the denominator. Loss of subjects to follow-up and withdrawal for a reason unrelated to safety or tolerance will not be considered as AEs. The ER of occurrence of any TEAE will be transformed to the number of subjects needed to treat (NNT) to observe one more subject with a TEAE in the acoziborole group compared with placebo (NNT=1/ER). The Cochran-Mantel-Haenszel test, stratified by study centre, will be used to compare the occurrence rate of TEAEs between treatment groups. The same test will be applied to the primary endpoint and each component of the composite endpoint (common TEAEs based on PTs).

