## 10.2. Definition of study populations included in the analysis

For the main safety study, the study population that will be used for the analyses is defined as below:

• **Safety set of subjects** (SS) is a modified intent to treat (mITT) set of subjects composed of all randomised subjects who received at least one tablet of IP (placebo or acoziborole).

For the TrypSkin sub-study, the study populations that will be used for the analyses are:

- **Primary set of subjects** for exploratory efficacy analyses is the mITT set composed of subjects, who participate in the TrypSkin sub-study and who receive at least one tablet of IP (placebo or acoziborole).
- Secondary set of subjects for exploratory efficacy analyses is the set of all seropositive subjects who are positive for the presence of trypanosomes by at least one molecular diagnostic test in the skin, blood and/or DBS at baseline.

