#### Sensitivity analysis

The main sensitivity analysis will be performed on the subgroup of positive dermal trypanosome subjects at entry.

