3.1. Confidence Intervals and p-values

All calculated p-values will be two-sided and compared to a 5% significance level. If a p-value is less than 0.05, the corresponding treatment group difference will be denoted as statistically significant. All estimates will be presented with two-sided 95% confidence intervals. No

adjustments of type one error for multiplicity testing are planned because the goal of the trial is to detect any potential safety issues instead of confirming and investigating a safety concern.

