5.3. Exploratory Objectives (Sub-study) Analysis

5.3.1. Exploratory Analysis

The primary set of subjects for exploratory efficacy analyses is the Safety set composed of subjects who participated in the TrypSkin sub-study. The primary exploratory objective is to establish whether acoziborole reduces the occurrence at 4 months of dermal trypanosomes in comparison with placebo. The exploratory efficacy will be evaluated using diagnostic and clinical endpoints. The primary diagnostic endpoint will be dermal trypanosome positive if TgSGP-PCR in skin is positive and the clinical endpoint will be the occurrence/presence of dermatitis and/or pruritus symptoms at 4 months. The occurrence rate of positive dermal trypanosome at 4 months based on the primary diagnostic parameters will be the primary measure of interest because the sample size is under control, and it corresponds to a measure of the level of potential transmission of reservoirs. The magnitude of the treatment effect will be the odds ratio of positive dermal trypanosomes. A Cochran Mantel Haenszel test using sites as strata will be used to compare acoziborole and placebo occurrence rate at 4 months of positive dermal trypanosome as well as occurrence of dermatitis and/or pruritus symptoms. In case of small proportions, the exact Cochran-Mantel-Haenszel (CMH) test will be performed. The Breslow-Day test of homogeneity of the odds ratio across sites will be performed to assess the generalizability of the treatment effect. If the test is significant, a forest plot will be provided to display the heterogeneity of the magnitude of treatment effect across sites and to detect sites explaining the heterogeneity.

As the odds ratio is not easy to interpret when the rate of positive subjects in the placebo group is not small ($P_0 > 0.05$), the odds ratio (OR) will be converted into the risk ratio (RR) using the following formula:

$$RR = \frac{P_1}{P_0} = \frac{OR}{(1 - P_0) + P_0 \times OR)}$$

where P_1 and P_0 are the estimated proportions of positive subjects in the acoziborole group and placebo group respectively. The excess rate $(P_1 - P_0)$ will also be estimated as a secondary measure of the magnitude of the treatment as well as the NTT (number of subjects needed to treat to get one less positive subject at 4 months in acoziborole group. The exploratory efficacy analysis results will be presented and individual data listing.

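### The TrypSkin baseline-positive subgroup has conflicting entry rules, and the broad ones admit subjects already negative on the skin TgSGP-PCR endpoint, so the excess rate, NNT and OR depend on the rule used

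*SAP*

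**What the plan says.** Four descriptions of the baseline-positive set are in force.

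- **Protocol Summary, Planned analyses:** positive for *T.b. gambiense* "by at least one molecular diagnostic test in the skin , blood and/or DBS at baseline".
- **Protocol 10.2:** "positive for the presence of trypanosomes by at least one molecular diagnostic test in the skin, blood and/or DBS at baseline". The species restriction is gone.
- **SAP 3.4.3 and 5.3.2:** positive "by at least one method in skin, blood and/or DBS at baseline". The test need no longer be molecular, so IHC counts, and 5.3.2 gives the organism as *Tb spp.*
- **Protocol 10.8, Sensitivity analysis:** "The main sensitivity analysis will be performed on the subgroup of positive dermal trypanosome subjects at entry". SAP 5.3.2 says the same: "the main sensitivity analysis will be performed on the subgroup of positive dermal trypanosome subjects at entry".

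Dermal positive has a definition of its own. SAP 5.3.1 states: "The primary diagnostic endpoint will be dermal trypanosome positive if TgSGP-PCR in skin is positive". Protocol 10.8 (Primary diagnostic parameter) agrees. SAP 5.3.2 adds that the analysis in this set is the same as the primary one, and that it is repeated for skin, blood and DBS separately.

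**The concern.** The first three rules differ on species and test type, and all three accept a positive result in any sample. The fourth is narrower: skin, one test. SAP 5.3.2 uses the third and fourth as if they were one population, so a programmer cannot derive a single set from the text.

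The stated objective is elimination of dermal *T.b. gambiense* (Protocol 2.1.3, SAP 1.2.1). A subject negative on skin TgSGP-PCR at baseline cannot show elimination on that test at Month 4. The first three rules all admit such subjects, for example someone positive only in blood or DBS. The mismatch is built into the testing sequence: Protocol 8.4 runs TgSGP-PCR only on samples already positive by TBR-PCR or 18S-PCR, which detect *T. brucei s.l.*, so a screening-positive, TgSGP-negative result is an expected outcome. Protocol 10.8 also says that the current specific molecular tests have low sensitivity.

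At stake are the size and precision of the reported effect in this subgroup, and the freedom to choose among four sets after results are seen.

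**Working it through.** **1. The plan's own figure.** Protocol Table 7 and SAP Table 2.4.3.1 take 20% positive at Month 4 on placebo, 1% on acoziborole (0.05 × 20%), and 175 v 525 subjects. Power at two-sided 5% is 99.99996% by the normal approximation and 99.99998% by Fisher enumeration, against 99.99% stated, so it reproduces. It covers the whole sub-study; the documents give no figure for the baseline-positive set.

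**2. Set-up.** Take 20% of 700 = 140 subjects in the set, 35 placebo and 105 acoziborole at 3:1. The plan's 20% is for detection in skin; using it for the any-method set is an assumption. Let f be the share of the set that is skin TgSGP-PCR positive at baseline (not in the documents). With no placebo effect and a 95% drug effect (both the plan's assumptions), and perfect repeatability (assumed):

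- Month 4 positive: placebo f, acoziborole 0.05f
- Difference = 0.95f; NNT = 1/(0.95f); RR = 0.05f/f = 0.05

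| f | Placebo v acoziborole | Difference (points) | NNT | OR | Fisher power, 35 v 105 |
|---|---|---|---|---|---|
| 1 | 100% v 5% | 95 | 1.05 | 0 | about 100% |
| 0.5 | 50% v 2.5% | 47.5 | 2.1 | 0.026 | about 100% |
| 0.25 | 25% v 1.25% | 23.75 | 4.2 | 0.038 | 98.8% |
| 0.1 | 10% v 0.5% | 9.5 | 10.5 | 0.045 | 66.9% |

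The SAP's OR-to-RR formula confirms the last identity: at f = 0.25, 0.038/(0.75 + 0.25 × 0.038) = 0.05.

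**3. Precision at f = 0.25.** The same-test set is 0.25 × 140 = 35 subjects, or 8.75 v 26.25 at 3:1. Standard error = √[p0(1−p0)/n0 + p1(1−p1)/n1].

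- Perfect repeatability: same-test √(0 + 0.05 × 0.95/26.25) = 4.3 points on 95, a ratio of 0.04. Any-method √(0.25 × 0.75/35 + 0.0125 × 0.9875/105) = 7.4 points on 23.75, a ratio of 0.31.
- If only 50% of true positives are detected again (assumed): same-test, 50% v 2.5%, gives 17.2 points on 47.5, a ratio of 0.36. Any-method, 12.5% v 0.625%, gives 5.6 points on 11.9, a ratio of 0.48.

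Relative to the effect, the any-method set is the less precise in both cases. In absolute points, the same-test interval is the wider one once repeatability is poor.

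**4. How low f could go (assumed rates).** Suppose k other tests each have an independent false-positive rate e. They admit a fraction 1 − (1−e)^k of the TgSGP-negative subjects. With e = 1% and k = 15 that is 14%, so at 20% TgSGP positivity f = 0.20/(0.20 + 0.80 × 0.14) = 0.64. Over e = 0.5% to 2% and k = 5 to 15, 1 − f runs from 9% to 51% at 20% positivity and from 55% to 93% at 2%.

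**5. The repeat by sample type.** The skin-only repeat removes subjects positive only in blood or DBS. It keeps those positive in skin by TBR-PCR, 18S-PCR, IHC or a novel test but negative on TgSGP-PCR.

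**The case against.** The strongest reply is that the right set is already there. Protocol 10.8 puts the main sensitivity analysis on dermal-positive subjects, and its own definition of dermal positive is skin TgSGP-PCR. That reading is fair for 10.8 alone. It does not rescue SAP 5.3.2, which merges that set with the any-method one, or the population definitions in Protocol 10.2 and SAP 3.4.3.

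A broad set is also defensible. With a specific test of low sensitivity, it keeps infected subjects whom TgSGP-PCR missed, and it is enriched compared with the all-subject primary analysis. This supports keeping it as a supplementary set, not treating it as the dermal-positive one.

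Same-test matching has its own weakness. Selecting on one positive result from an imperfect test makes some placebo subjects turn negative by chance: half of them at 50% re-detection. The set may also be very small.

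Three stronger readings are tempting, and the documents do not support them:

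- **That placebo would be reported with a false clearance rate.** No clearance rate is planned. The measure is Month 4 occurrence compared between arms. Clearance appears only if a reader takes Month 4 negatives in this set as cleared.
- **That this would make the test look poorly repeatable.** Protocol 10.8 and SAP 5.3.6 assess baseline to Month 4 association for each test on placebo data. A subject TgSGP-negative at both visits has not changed status on that test.
- **That one arm gains.** The set is fixed at baseline, so both arms are diluted alike.

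**Conclusion.** The point holds as a conflict of definitions with a real effect on the subgroup estimates. Four entry rules exist, SAP 5.3.2 treats two of them as one, and the fault is shared by both protocol set definitions. The broad rules shrink the excess rate, raise the NNT, move the OR (which SAP 5.3.1 names as the magnitude of effect) and reduce precision relative to the effect. They leave the RR at 0.05 under the plan's assumptions.

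The size is not known. It rests on f, which is assumed throughout, and the 95-point figure also needs perfect repeatability, which Protocol 10.8 itself leaves open. This is a sensitivity analysis in an exploratory sub-study. It should be corrected, but nothing in the primary safety analysis depends on it.

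**What to change.** Use one definition in the Protocol Summary, Protocol 10.2 and 10.8, and SAP 3.4.3 and 5.3.2. For each endpoint test, the main sensitivity set is dosed TrypSkin subjects positive at baseline on that same test in the same sample type; for the primary parameter, that is TgSGP-PCR in skin. Keep the any-method set as a separately labelled supplementary analysis, and state that Month 4 negatives in it are not to be read as cleared.

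The cost is wording in both documents and one further table. State the downside too. If 35 subjects are TgSGP-positive at baseline, about 9 are on placebo (35/4 = 8.75), spread over site strata, so exact methods are needed. With an imperfectly repeatable test, some of those placebo subjects will turn negative by chance, and the text should say so.

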5.3.3. Comparability of treatment groups

To assess whether randomization provided comparable treatment groups, randomized groups will be compared using descriptive statistics at baseline and more precisely the proportion of dermal trypanosome positive subjects at baseline and proportion of subjects with dermatitis and/or pruritus at baseline will be compared using chi-square (χ^2) test as a measure of deviation from perfect comparability.

5.3.4. Interpretability of results

The knowledge of the change of status between baseline and 4 months is helpful to interpret results. If in the placebo group a large proportion of subjects change their status from negative to positive and positive to negative, then the predictive validity of the diagnostic test is questionable (see secondary analysis of the primary endpoint).

Moreover, the positive association at baseline between dermatitis or pruritus symptoms and positive dermal trypanosome test will be assessed using the Cramer V coefficient and both treatment groups. In the presence of a significant association, both the clinical effect of acoziborole and the clinical validity of the dermal tryp test will be strengthened. The Cramer V coefficient measure is defined as¹⁰:

$$V = \sqrt{\frac{\chi^2}{nt}}$$

Where χ^2 is the chi-square statistics, *n* is the sample size, *t* is the smaller of the number of rows minus one or the number of columns minus one. If *r* is the number of rows, and *c* is the number of columns, then t is given as

$$t = Minimum (r - 1, c - 1).$$

Cramer's V equals 0 when there is no relationship between the two variables, and generally has a maximum value of 1, regardless of the dimension of the table or the sample size. This makes it possible to use Cramer's V to compare the strength of association between any two cross classification tables. Tables which have a larger value for Cramer's V can be considered to have a strong relationship between the variables, with a smaller value for V indicating a weaker relationship.

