5.3.5. Multiplicity of testing

Due to the exploratory nature of the sub-study, no adjustment for multiplicity of testing will be done. The level of the p-value will be used to assess the strength of the findings.

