5.3.6. Properties of diagnostic tests Analysis

Considering successively the results of (1) TgSGP-PCR in skin (primary diagnostic parameter), and (2) IHC, TBR-PCR and/or 18S-PCR in skin (secondary diagnostic parameters), as validated diagnostic methods, the relative specificity, relative sensitivity, positive and relative negative predictive values of multiplex qPCRs, multiplex RT-qPCRs and SHERLOCK on skin, blood and DBS will be analyzed at enrolment. Four analyses will be performed for skin, blood, DBS and considering the result of any of the three samples.

Based on the placebo group data, the association between baseline and 4 months diagnosis results will be estimated through Cramer V coefficient for each diagnostic test and combination of diagnostic tests. The test or combination of tests providing the best association (reproducibility of baseline result) will be used for ranking tests. Other properties: relative sensitivity, relative specificity, predictive values, Cohen Kappa coefficient will also be used for ranking tests alone or in combination. Multicriteria ranking (sum of ranks) will be performed and the primary analysis will be redone on this new reference (best multicriteria rank) and each diagnostic test property will be computed with respect to this new reference.

6. Statistical software

All statistical analyses and generation of TLFs will be done using SAS software. Copyright © 2016 SAS Institute Inc¹¹.

7. Shell Tables, Listings and Figures (Attached separately)

8. References

- 1. International Conference on Harmonisation; Guidance on Statistical Principles for Clinical Trials *E9; Availability--FDA. Notice.* Vol 63.; 1998.
- 2. International Conference on Harmonisation: Structure and Content of Clinical Study Reports E3, Japan and USA.; 1995.
- 3. Investigator Brochure Acoziborole V4.0 12 November 2019.

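### SAP 5.3.4 sets out to assess a positive symptom–test association with an unsigned statistic and a rule that names no direction, and it reads a pre-dose association as support for the drug's clinical effect

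*SAP*

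**What the plan says.** SAP 5.3.4 states that "the positive association at baseline between dermatitis or pruritus symptoms and positive dermal trypanosome test will be assessed using the Cramer V coefficient", using both treatment groups. The reading rule follows: "In the presence of a significant association, both the clinical effect of acoziborole and the clinical validity of the dermal tryp test will be strengthened".

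V is defined as the square root of chi-square/(n t), where t "is the smaller of the number of rows minus one or the number of columns minus one". On its range, the SAP says "Cramer's V equals 0 when there is no relationship between the two variables, and generally has a maximum value of 1". Section 5.3.4 names no odds ratio, signed phi or check of direction.

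Two general rules bear on how the result is read. SAP 3.1: "All calculated p-values will be two-sided and compared to a 5% significance level". SAP 5.3.5, for the sub-study: "The level of the p-value will be used to assess the strength of the findings".

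Cramer's V appears again in SAP 5.3.6, between baseline and month-4 results in the placebo group: "The test or combination of tests providing the best association (reproducibility of baseline result) will be used for ranking tests". That section also lists Cohen's kappa among the other ranking properties. Protocol 10.8 uses V for the same ranking but does not list kappa, and it has no symptom association analysis that could supply a direction.

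**The concern.** There are two faults in 5.3.4 and one lesser point in 5.3.6.

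- **No direction.** The stated target is directional, but neither the statistic nor the rule is. V measures strength only, the test is two-sided, and the rule is met by any significant association. Symptoms that were significantly less common in test-positive subjects would meet the words of the rule, although such a result would count against the clinical validity of the test.
- **An inference the data cannot carry.** The rule says the same baseline association strengthens the clinical effect of acoziborole. Baseline precedes randomisation (SAP 2.7.1), so no subject has yet been dosed and the association contains no comparison of drug with placebo. This holds even if the association is positive.
- **Lesser point.** Reproducibility is agreement between two readings, whereas V measures association. The ranking in 5.3.6 selects a new reference on which the primary exploratory analysis is repeated, so the choice of measure has some consequence there.

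**Working it through.** The plan states no figure for this analysis, so there is none to reproduce. The check applies the SAP's formula to example tables.

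**Inputs.** n = 690 evaluable (SAP 2.4.2); 20% dermal-positive at baseline (SAP 2.4.3), so 0.20 × 690 = 138 positive and 552 negative; two-sided 5% (SAP 3.1); t = min(2−1, 2−1) = 1. The documents give no symptom rates. I assume 115 symptomatic subjects (16.7%), which makes the expected number of symptomatic positives 138 × 115/690 = 23, and then move 12 subjects either way.

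**Formulas**, for a table [[a, b], [c, d]] with rows test-positive and test-negative, and columns symptoms yes and no:
- chi-square = n(ad − bc)² / (product of the four margins), without continuity correction
- V = √(chi-square/n)
- phi = (ad − bc) / √(product of the margins)
- OR = ad/(bc), with log-scale 95% CI

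| | Direct [[35,103],[80,472]] | Inverse [[11,127],[104,448]] |
|---|---|---|
| Symptoms, positives v negatives | 25.4% v 14.5% | 8.0% v 18.8% |
| ad − bc | +8280 | −8280 |
| Chi-square, p | 9.39, 0.0022 | 9.39, 0.0022 |
| V | 0.117 | 0.117 |
| phi | +0.117 | −0.117 |
| OR (95% CI) | 2.00 (1.28 to 3.15) | 0.37 (0.19 to 0.72) |

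The sign is lost when ad − bc is squared. V and p are identical, so the written rule treats the two tables alike, while phi and the OR separate them. With continuity correction both tables give V = 0.112 and p = 0.0033. A pair that is not mirrored behaves similarly: 14/138 v 110/552 gives OR 0.45, V = 0.102, p = 0.007; 40/138 v 110/552 gives OR 1.64, V = 0.088, p = 0.021. At n = 690, any V of at least √(3.841/690) = 0.075 is significant.

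**How often the literal rule would be met by an inverse result** (100,000 simulated trials per scenario, n = 690, assumed symptom rates):
- No association, 20% symptomatic in both groups, 20% positivity: the rule is met in 4.9% of trials, and the inverse direction accounts for 2.3% of all trials.
- True inverse association, 10% in positives v 20% in negatives: met in 26.6%, 82.5% and 88.6% of trials at 5%, 20% and 25% positivity, essentially all inverse. Requiring OR > 1 as well brings these to about 0%.

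**Reproducibility in 5.3.6.** Take 175 placebo subjects (SAP 2.4.3), 35 of them positive at baseline; rows are baseline, columns month 4.
- Test A, [[35,0],[35,105]] (positivity rises from 20% to 40%): V = 3675/√(35 × 140 × 70 × 105) = 0.612. Observed agreement is 140/175 = 0.80, chance agreement (35 × 70 + 140 × 105)/175² = 0.56, and kappa = 0.24/0.44 = 0.545.
- Test B, [[24,11],[11,129]] (positivity stays at 20%): V = 2975/(35 × 140) = 0.607. Observed agreement is 153/175 = 0.874, chance agreement (35² + 140²)/175² = 0.68, and kappa = 0.607.

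V ranks A first and kappa ranks B first. When the margins are equal and agreement exceeds chance, the two measures coincide: [[25,10],[10,130]] gives 0.643 for both.

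**The case against.** The strongest reply is that the SAP does name the direction. It speaks of a positive association, and the next sentence can be read as referring back to it. V is computed from a 2×2 table whose counts show the direction, and the table shells are attached separately, so we cannot say those counts will go undisplayed. The only hypothesis in the documents (protocol 10.8) is that dermal trypanosomes may cause the symptoms, and the inverse scenarios rest on assumed rates. All of this stands. A reader might infer that the plan would in practice report an inverse association as support for the test and the drug. The documents do not show that; they show a rule that fails to exclude it.

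On the clause about the drug, it can be said that 5.3.4 concerns interpretability, and that a baseline link makes it more plausible that a fall in symptoms reflects parasite clearance. That is a fair reason to look at the link, but it is an argument about mechanism and test validity. The clinical effect is assessed by the month-4 CMH comparison of dermatitis and pruritus in SAP 5.3.1, which the baseline association neither enters nor alters.

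On reproducibility, a reader might infer that V alone chooses the reference test, or that a test whose results reverse would rank best. The text does not support either. SAP 5.3.6 sums ranks over several properties including kappa, and 5.3.4 already treats many changes of status in the placebo group as a warning. Complete reversal gives V = 1 only near 50% positivity; at 20%, the most extreme inverse table, [[0,35],[35,105]], gives V = 0.25. Under the plan's own assumption of 20% positivity in placebo at both times, V and kappa agree whenever agreement exceeds chance. This part is therefore minor.

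**Conclusion.** The concern holds for 5.3.4, within limits. As defined, statistic and rule cannot distinguish a direct from an inverse association; this follows from the SAP's formula and needs no assumed rates. The assumed rates affect only how often it would matter: rarely if there is no association (about 2% of trials), and often only if the truth is inverse. The statement that the association strengthens the clinical effect of acoziborole is unsupported whatever the direction, because the data are pre-dose and hold no treatment contrast. The ranking by V in 5.3.6 is a lesser matter that arises when placebo positivity shifts between the two visits.

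The scope is small. This is an interpretive aid in an exploratory sub-study, and neither the primary safety analysis nor the month-4 CMH test on TgSGP-PCR depends on it.

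**What to change.** In SAP 5.3.4:
1. Report the odds ratio (or signed phi) with its 95% CI for the baseline association; V may stay beside it as a measure of strength.
2. State that the result supports the clinical validity of the dermal test only if the odds ratio exceeds 1 and the CI excludes 1.
3. Delete the clause saying that the association strengthens the clinical effect of acoziborole, and refer instead to the month-4 comparison in 5.3.1.

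Optional, in SAP 5.3.6: use kappa, which is already listed there, rather than V as the reproducibility criterion.

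The cost is SAP wording and a small programming change. Every quantity comes from the same 2×2 tables, and no new data are needed.
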